**b. Recruitment Sources**

We plan to enroll 10 women who meet criteria for history of MDD, have decided to stop AD medication while trying to conceive or during early pregnancy (< 28 weeks), and are eligible to receive treatment with EnBrace prenatal supplement. We also plan to enroll 10 women who meet the criteria for a current major depressive episode who are trying to conceive or pregnant (< 28 weeks), and are eligible to receive treatment with EnBrace prenatal supplement.

Potential subjects will be enrolled from four major sources:

- 1) Women who have had a previous interaction with the MGH Center for Women's Mental Health, either through research or clinically, and have consented to be contacted about future studies for which they may be eligible.
  - a. These women will be contacted by e-mail, postal mail, and phone, based on how each indicated she would prefer to be contacted by our program.
- 2) Women who are currently seen in consults who indicate to the MGH Perinatal Psychiatrist with whom they have a consult that they would be interested in adjunct or alternative medication for pregnancy
  - a. These women will be given information about the study at the end of their consult with a Perinatal Psychiatrist and asked to schedule a separate appointment for a screening interview with a member of the study staff
- 3) Women who are seen in the MGH outpatient Obstetrics department
  - a. These women will be pre-identified through preliminary screening, and approached during their clinic visit by a provider in the Obstetrics department who will introduce the study and obtain permission to be contacted by study staff.
- 4) Physicians in the community

As a group, clinicians at the MGH Center for Women's Mental Health (CWMH) have extensive experience over the last 25 years providing these consultations to women presenting for the most current information regarding both risks of AD exposure during pregnancy and risks of recurrence of underlying disorder in the setting of AD discontinuation either while planning to conceive or during pregnancy. This group, under the direction of [name], has a longstanding record of recruiting women for federally funded studies of depression before, during and after pregnancy derived from a potential subject pool of 900 pregravid women per year who are seen for consultation regarding the risks of psychotropic use during pregnancy. Approximately half (450) of these women are euthymic on maintenance AD therapy and are referred by their community clinicians for consultation about maintaining, changing, or discontinuing their medication for pregnancy.

During consultations by perinatal psychiatrists, the relative risks of fetal exposure to ADs are explained, as are the attendant risks of relapse/recurrence of depression in the setting of AD discontinuation. Information about the relative risks of various treatment options is provided to both the patient and the referring clinician; referring psychiatrists are contacted both by phone and in writing. Available information informing patient decisions about treatment options and the associated risk/benefit analysis is also available to patients/potential subjects through a web driven Perinatal Information Resource Center ([www.womensmentalhealth.org](http://www.womensmentalhealth.org)), run by the MGH Perinatal and Reproductive Psychiatry Program. Patients and clinicians are consistently referred to this dynamic website, which is constantly updated with the most recent data.

## Partners Human Research Committee Detailed Protocol

As part of MGH IRB approved protocol 2002P001596, patients seen in consultation may consent to be contacted over time to monitor their plans and ultimate treatment decisions regarding AD use prior to and during pregnancy. Over the course of several years, we have established a very large cohort of women with perinatal depression and euthymic women on AD treatment of whom ultimately 50% decide to discontinue treatment prior to and during pregnancy. The pool of study-eligible subjects for the current investigation is therefore substantial; given this system, accessioning an adequate number of subjects for the pilot is assured.

At the point of enrollment, potential subjects will have already reviewed risks of perinatal treatment in a consultation with a non-study psychiatrist in the CWMH program and in collaboration with the patient's psychiatrist in the community, decided to discontinue AD treatment (Group 1) or begin antidepressant monotherapy or supplement current AD treatment (Group 2).

Consultations presenting to the CWMH are reviewed on a weekly basis by the team of the CWMH perinatal psychiatrists to provide consistency in what information is conveyed. *No subject will be referred to the study for potential inclusion until she has made an informed decision regarding AD therapy.*

Potential subjects will also be recruited through outpatient centers of the Department of Obstetrics at the Massachusetts General Hospital. Study staff will first identify potentially eligible patients prior to their appointments in the clinic and inform their health care provider that they may be eligible. The provider who is known to the potential subject and has firsthand knowledge of the patient's medical history will initially introduce the study to the patient and obtain the patient's verbal consent to be contacted or approached by study staff.

### IV. SUBJECT ENROLLMENT

#### a. Methods of enrollment

Potential subjects will be recruited from the Massachusetts General Hospital (MGH) Center for Women's Mental Health (CWMH) clinic, outpatient Obstetrics clinic, and from referrals from health care providers in the community. Interested potential participants will be referred to study staff for a pre-screening phone call. Patients potentially eligible for Group 1 will continue on in the screening process only if the patient explicitly states that she has decided to discontinue antidepressant treatment in the context of pregnancy (planning or during). Patients potentially eligible for group 2 will only continue the screening process if they state that they do not wish to start therapy with an antidepressant medication.

After a preliminary phone screening, a research coordinator working within the CWMH will schedule the patient for a baseline visit. This baseline visit will be conducted by either the principal investigator (PI) or another clinician trained in all study assessment procedures, along with trained clinical research coordinators. After an explanation of the study procedures, written informed consent will be obtained from patients prior to execution of any study assessments or procedures.

#### b. Informed Consent procedures

The study coordinator will briefly discuss the main eligibility criteria and study protocol with each woman who inquires about the study at the time of a brief phone screen. At the baseline visit, a study coordinator and licensed study physician will review the consent form in its entirety with prospective subjects. Women enrolling in this study must be capable of understanding the nature of this study as well as the discomforts and potential benefits. Any questions or areas of concern regarding the protocol

[figure not shown]
## Partners Human Research Committee Detailed Protocol

or alternative treatment options will be addressed by one of the study physicians. If a woman feels comfortable with the study procedures, she will sign two copies of the consent form along with the study physician.

Enrolled subjects will be given a copy of the completed consent form before any study procedures are completed. If subjects have reservations about study participation at the first visit, they have the option to take the consent form home to review the decision to participate in the study with their family and health-care providers, and then return at a later date to discuss the study again with research physicians and coordinators before signing the consent form and initiating study procedures. Subjects may also elect to participate in the study remotely by phone for visits 2, 3, 5, and 6, for which verbal consent will be recorded in the subject binder. Subjects will be made aware that visits 1, 4, and 7 must be in person before signing the consent form.

### **STUDY PROCEDURES**

Patient Flow through Study Procedures:

Procedures/Data Collection

For the acute treatment phase, visits will include a baseline visit (2-3 hours), and every other week assessments (thirty minutes to one hour each). Please note that the schedule of independent outcome assessments and in-person visits may vary depending on patient scheduling issues. Furthermore, research personnel will attempt to schedule all assessments as in-person visits, however to accommodate subjects, assessments may be done over the phone.

Participants may elect to participate in visits 2, 3, 5, and 6 via phone interview rather than in-person visits. All participants must participate in visits 1, 4, and 7 in person. Study physicians will perform clinician-administered questionnaires by telephone for participants who elect to participate remotely for visits 2, 3, 5, and 6. Verbal consent will be obtained from the subject to conduct visits by phone and will be recorded in the subject's research file. Those subjects who choose to participate in visits 2, 3, 5, and 6 will receive the study drug by mail using first-class shipping to ensure appropriate dispensing and supply of the study drug over the course of the study.

Additionally, patients may request a physician meeting at any visit. Please see table below for listing of assessments at each visit.

**Schedule of Assessments: Acute Phase (12 weeks)**

Visit #	V1	V2	V3	V4	V5	V6	V7
Week #	0	2	4	6	8	10	12
MINI: full MINI at V1; depression module at follow-ups	X	X	X	X	X	X	X
Demographics, medical & psychiatric history	X						
Labs: genetic sample	X						
Labs: folate, homocysteine, B12, IL-6, CRP	X			X			X
Vital Signs: Height only at V1, weight, blood pressure	X	X	X	X	X	X	X
MADRS	X	X	X	X	X	X	X
CGI-Clinician	X	X	X	X	X	X	X
EPDS	X	X	X	X	X	X	X
QIDS-SR	X	X	X	X	X	X	X
Q-LES-Q-SF	X			X			X

A Qualitative interview will be conducted by study staff after completion of the acute treatment phase in order to obtain feedback on the intervention.

Instrument Descriptions:

## Partners Human Research Committee Detailed Protocol

*Mini-International Neuropsychiatric Interview (MINI)*: The MINI is a widely used clinician-administered, structured interview used to diagnose psychiatric patients. It was designed to rapidly and accurately assess psychiatric illness, and has been found to be reliable and valid in making a diagnosis of MDD and other psychiatric diagnoses(73-75). The MINI can be administered by non-clinicians who are trained to administer it and the MDD section takes up to 10 minutes to complete.

*Montgomery-Åsberg Depression Rating Scale (MADRS)*: The MADRS is a widely used 10-item clinician-rated scale that describes the severity of depressive symptoms (range  $\geq 60$ , higher score indicates more depression symptoms)(76). The MADRS has good internal consistency (Cronbach's  $\alpha = 0.82$ ), test-retest reliability (correlation 0.90), and validity and is highly sensitive to changes with treatment(76-78). Remission of depression in clinical trials has been defined loosely as a final MADRS score  $<10$  or, more strictly, as a score  $<5$ (79).

*Clinical Global Impressions Scale (CGI)*: The CGI contains 7-point global severity and change (improvement) scales and will be used as an overall outcome measure(80).

*Quick Inventory of Depressive Symptoms (QIDS-SR)*: The QIDS-SR is a 16-item self report rating scale for depressive symptoms. This instrument was used in the STARD effectiveness trial, in which  $>4000$  depressed patients were enrolled. In a recent paper, Trivedi and colleagues reported on the psychometric properties of the QIDS-SR, including documentation of high concurrent validity and internal consistency(81).

*Edinburgh Postnatal Depression Scale (EPDS)*: This measure is a 10-item self-report used to measure postpartum depressive symptoms and takes  $<5$  minutes to complete(82). This scale will be one of our outcome measures for depressive symptoms. It has been validated in community and obstetrical samples. A score of  $\geq 10$  is suggestive of perinatal depression. Because it measures symptoms and is not diagnostic of a relapse, we will use the MINI to assess the recurrence of a major depressive episode. The EPDS is widely utilized in multidisciplinary settings and de-emphasizes somatic symptoms that are common in pregnancy and postpartum. The EPDS is validated for use in pregnancy as well as postpartum with good specificity and sensitivity(83).

*Quality of Life Satisfaction Questionnaire Short Form (Q-LES-Q-SF)*: The Q-LES-Q asks questions in 8 modules of 6-16 questions each, about physical health/activities, general feelings of well being and relaxation, function at work, household duties, school or course work, leisure activities, social relations, and general activities over the past week(84). The "short form" includes only the General Activities section. Patients are asked to rate the answers on a scale of 1-5, from "not at all or never" to "frequently or all the time." Answers in the "frequently" range indicate greater satisfaction with life. A total score for the "short form" is calculated by simply totaling answers to all 16 items of the General Activities section.

### Laboratory Measures

Blood samples will be collected for laboratory analyses that may serve as biomarkers of treatment response. These include levels of biologic measures that are associated with folate metabolism and inflammatory markers that may be associated with omega-3 fatty acid intake (known to be anti-inflammatory). The following will be assessed at baseline, 6 weeks, and 12 weeks: folate, B12, and homocysteine levels; IL-6 and CRP, inflammatory markers. Cheek swab samples for genetic testing will be collected at baseline for polymorphisms associated with folate metabolism (i.e., genes encoding for MTHFR, methylene tetra-hydro folate reductase).

### Drop criteria:

## Partners Human Research Committee Detailed Protocol

1. Participant experiences severe worsening of depression symptoms, as indicated by a CGI-I of 6 or 7 on 2 consecutive visits determined by a licensed study psychiatrist. Subjects with a CGI-I of 6 or 7 on 2 consecutive visits will be terminated from the study and referred for additional clinical treatment as needed.
2. A Group 1 participant who is not experiencing depression symptoms decides to restart antidepressant treatment while they are well
3. A Group 2 participant who enrolled during a current depressive episode has either started a new antidepressant or increased the dose of an antidepressant they were already taking
4. Emergence of suicidal ideation, homicidal ideation, or psychotic symptoms. The anchors for suicidality will include the QIDS-SR, Question 12 (with an answer of 2 or 3) and the MADRS, Question 10 (with an answer of 4, 5, or 6). Acute suicidality, based on these measures and the licensed psychiatrist's clinical assessment, will result in termination of participation in the study and swift triage to the Acute Psychiatry Service at Massachusetts General Hospital.
5. Evidence of abuse or misuse of study medication
6. Evidence of current alcohol and/or drug abuse
7. Any severe or unstable medical illness that includes concern regarding safety of continued use of study medication
8. Intolerance to study medication as determined by research clinician
9. Significant hypersensitivity reaction
10. Inability or unwillingness to complete the study procedures

## V. BIOSTATISTICAL ANALYSIS

We will compare the rates of depressive relapse and duration of time out of a depressive episode for Group 1 participants, and compare these data to historical controls that were also assessed prospectively. For Group 2, we will compare depressive response rates (response defined as 50% reduction in depressive symptoms on the MADRS, our primary outcome) to response rates in studies of SSRIs for the treatment of depression.

In addition, we will monitor depressive symptom burden with continuous variables across the treatment study for both groups.

To control for prenatal vitamin (PNV) use, we will supply a standard PNV to each participant to take daily in combination with EnBrace. The Sponsor has offered to supply the PNV, such that each participant will take the same PNV; this will lower the risk of inconsistencies between participants. In the statistical analysis, the data collected in this preliminary study will be compared to historical controls with a history of MDD who discontinued AD maintenance therapy during pregnancy, most of which were taking standard PNVs, but not EnBrace. This reference will allow us to estimate the relative efficacy of EnBrace in relapse prevention of women who discontinue maintenance ADs for pregnancy.

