## Partners Human Research Committee Detailed Protocol

have decided to stop ADs (Group 1). Relapse rates for women in this context have been demonstrated to be high, with 68% relapse rates in a large multisite NIMH-funded trial.

**Specific Aim 1b:** To evaluate the efficacy of EnBrace when used as an acute treatment for MDD in a group of women (N=10) who are trying to conceive or are early in pregnancy (Group 2). Women will have major depressive episodes in this group, and may receive EnBrace as monotherapy, or as an adjunct to current pharmacotherapy.

*Hypothesis 1a:* We hypothesize that relapse rates will be lower for women who receive EnBrace compared to historical controls. MDD relapse will be determined by the Mini-International Neuropsychiatric Interview (MINI) mood module that will be administered by a study clinician at each visit.

*Hypothesis 1b:* We hypothesize that the majority of women who receive EnBrace will experience a response (50% improvement in depressive symptoms) to EnBrace therapy.

**Specific Aim 2:** To identify biological markers as potential predictors of response to EnBrace.

*Hypothesis 2:* We hypothesize that pre- to post-treatment changes in homocysteine, folate, B12, IL-6 and CRP will be associated with response to EnBrace. We hypothesize specifically that levels of folate and B12 will increase and homocysteine will decrease temporally with treatment and be predictive of prevention of depressive episodes. We hypothesize that treatment will lower IL-6 and CRP levels due to the anti-inflammatory components of EnBrace (i.e., omega-3 fatty acids) and that decreased levels of inflammatory markers may predict lower risk of depressive relapse in participants who enter the study while not on a depressive episode (Group 1), and will predict response to treatment in women who enter the study while in a depressive episode (Group 2).

**Specific Aim 3 (Exploratory):** To identify factors influencing adherence to and tolerability of treatment. This will be achieved by using qualitative methods to explore (a) perceived risks and benefits of treatment; (b) perceived side effect profile; (c) treatment convenience; (d) knowledge of, attitudes towards, and preferences for depression treatment while attempting to conceive or early pregnancy.

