## VI. RISKS AND DISCOMFORTS

## Partners Human Research Committee Detailed Protocol

Subject burden for participation includes the time spent participating in study visits. Visits will include a baseline visit (2-3 hours), follow up visits (30 min to one hour each), and three blood draws over the course of the study. The total time burden for subjects is similar to our previous investigations involving very similar populations. Risks of this study include potential psychological distress that may occur during treatment and assessment visits, during which history, current symptoms and life stressors are discussed. Participation in this study does not directly affect risk for recurrence or worsening of depression. To be eligible, subjects must have already made an informed decision regarding antidepressant treatment in the context of pregnancy. Study assessment and treatment visits may increase recognition of symptom worsening and ensure that appropriate treatment is provided. Patients who experience worsening of depressive symptoms will be presented with options for treatment, including antidepressant medications.

According to the NIH National Library of Medicine, adverse reactions to EnBrace that have been reported include: allergic sensitization associated with folic acid; paresthesia, somnolence, nausea, and headaches associated with pyridoxine; and mild transient diarrhea, polycythemia vera, itching, transitory exanthema and the feeling of swelling of the entire body associated with cobalamin. Finally, EnBrace may cause allergic reaction. If patients have any side effects, they will be instructed to report them immediately to the study doctor. If any subject develops an adverse event, the adverse event will be reported to the MGH IRB consistent with Human Research Committee (HRC) guidelines. EnBrace carries no known risks to an embryo, fetus, or breastfeeding infant.

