## Partners Human Research Committee Detailed Protocol

discontinuing maintenance AD treatment will be described to the patient in detail. Additionally, the research clinician will inform the patient that they can choose, at any point, to reinitiate AD treatment.

For (2) prompt identification of patients who experience a depressive recurrence or worsening of acute depression during the study, it is likely that over the course of the investigation some women may have significant psychiatric symptoms requiring acute intervention and/or evaluation and referral. The investigators have the clinical expertise and resources available to provide acute evaluations and, if needed, referral. The Acute Psychiatry Service of the MGH is staffed and available 24 hours/day to handle psychiatric emergencies. Because subjects are assessed for mood symptoms at each study assessment visit, the likelihood that symptom worsening will be identified in a timely manner is increased.

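### A Group 1 woman who restarts an antidepressant for worsening short of a MINI episode can count as a non-relapse on EnBrace, and Section V does not show her separately

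*Combined protocol and SAP*

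**What the plan says.** Section V (Biostatistical Analysis) gives the Group 1 analysis: "We will compare the rates of depressive relapse and duration of time out of a depressive episode for Group 1 participants". The comparator is "historical controls with a history of MDD who discontinued AD maintenance therapy during pregnancy", and the stated purpose is: "This reference will allow us to estimate the relative efficacy of EnBrace in relapse prevention of women who discontinue maintenance ADs for pregnancy". The only other outcome analysis in the section is continuous monitoring of symptom burden in both groups.

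Relapse is defined in Section II, Hypothesis 1a: "MDD relapse will be determined by the Mini-International Neuropsychiatric Interview (MINI) mood module". The EPDS entry under Instrument Descriptions draws the same line. That scale measures symptoms, and for an episode "we will use the MINI to assess the recurrence of a major depressive episode".

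On restarting an antidepressant, the documents say three things:

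- Drop criteria, item 2, removes: "A Group 1 participant who is not experiencing depression symptoms decides to restart antidepressant treatment while they are well". Item 3 removes a Group 2 woman for any new antidepressant or dose increase, with no such limit.
- Section VI (Risks and Discomforts): "Patients who experience worsening of depressive symptoms will be presented with options for treatment, including antidepressant medications".
- Section VI, Protection Against Risk: women are told that "they can choose, at any point, to reinitiate AD treatment".

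The Schedule of Assessments has no item for antidepressant use. The prompt at each visit in Section VIII asks about health problems other than depression. Section V has no rule for a Group 1 woman who restarts.

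**The concern.** Together these rules leave one kind of woman unaddressed. She is in Group 1, worsens without reaching a MINI episode, accepts the antidepressant she is offered, and does not meet MINI criteria afterwards. No restart criterion removes her. Read literally, the outcome definition makes her a non-relapse, and her weeks after the restart count as time out of episode. If she restarted at week 4 (an assumed date), 8 of her 12 weeks would be spent on the resumed drug.

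The comparison is meant to estimate what EnBrace does in women who have stopped antidepressants, and she is no longer one of them. Her good outcome may be due to the antidepressant, and nothing in Section V commits the report to showing how many such women there were. The pilot has no decision rule, but Section II says that its data will be used to develop a randomized trial, where symptomatic restarts will have to be handled.

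**Working it through.** The plan states no test, power or sample-size derivation, so there is no figure of its own to reproduce. The check has two parts: whether any rule closes the gap, and how large the effect could be.

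**Does any rule remove or separate her?** Item 2 does not, because it requires that she is well and without symptoms. Item 3 does not, because it concerns Group 2. Item 1 needs a CGI-I of 6 or 7 at two consecutive visits, and item 4 needs suicidal, homicidal or psychotic symptoms, so these reach only severe cases. The MINI every two weeks finds her only if she becomes a case. That she stays in the study is inferred from the wording of item 2; no sentence says so directly.

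**Inputs from the documents.** N = 10 in Group 1 (Section II, Aim 1a). Relapse of 68% in women who discontinued (Section I and Aim 1a) and 26% in women who maintained treatment (Section I). Section I also gives over 43% for discontinuers, citing the same reference as the 68%.

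**Assumptions.** The benchmark *b* is the 12-week cohort risk without restarts, and the product is inert. *k* women restart for symptoms. They would have had risk *u* untreated and have MINI risk *r* after restarting. Antidepressants do not raise risk, so *r* ≤ *u*.

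The cohort risk without restarts has to stay at *b*. If the restarters are the higher-risk women, the others must therefore lie below *b*:

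- Risk in the others: (10*b* − *ku*)/(10 − *k*)
- MINI-only rate: (10*b* − *ku* + *kr*)/10 = *b* − *k*(*u* − *r*)/10
- Rate counting the first of an episode or a symptomatic restart: (10*b* − *ku* + *k*)/10 = *b* + *k*(1 − *u*)/10

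With *r* ≤ *u*, the MINI-only rate is never above *b* and the second rate is never below it. In expectation the two bracket the no-restart rate.

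**Example, *b* = 68%, *k* = 2, *u* = 90%.** The other eight women have risk (6.8 − 1.8)/8 = 62.5%.

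| Restarter MINI risk *r* | MINI-only | Shift from 68% |
|---|---|---|
| 26% | (5.0 + 0.52)/10 = 55.2% | −12.8 points |
| 80% | (5.0 + 1.60)/10 = 66.0% | −2.0 points |
| 90% | (5.0 + 1.80)/10 = 68.0% | 0 |

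The rate that also counts symptomatic restarts is (5.0 + 2)/10 = 70% in every row. With *k* = 0 all rates are 68%.

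**Dependence on the benchmark.** If the restarters are no different from the rest (*u* = *b*), then with *k* = 2 and *r* = 26% the MINI-only rate is 68 − 2 × (68 − 26)/10 = 59.6%, a shift of −8.4 points. With *b* = 43% it is 43 − 2 × (43 − 26)/10 = 39.6%, a shift of −3.4 points.

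**Against sampling error.** Each woman is 1/10, or 10 points. The exact (Clopper-Pearson) 95% interval for 6 of 10 is 26.2% to 87.8%, which is 61.6 points wide.

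**The case against.** The strongest reply is that counting MINI episodes regardless of later treatment is a legitimate outcome, stated in advance in Hypothesis 1a. It may also be the right match: if the historical study kept women who restarted among its discontinuers and counted only diagnosed episodes, MINI-only is the like-for-like definition. The group is narrow as well. A woman must worsen, restart, avoid the CGI-I and suicidality drops, and never meet MINI criteria at visits two weeks apart. Among ten women there may be none.

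All of that stands, and it is why the main rate should not change. Part of a further reply also stands. The MADRS, CGI, EPDS and QIDS-SR are taken at every visit, so the worsening itself is captured. But her scores after a restart also reflect the antidepressant, so symptom monitoring does not isolate her.

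Three stronger readings are tempting, and the documents support none of them.

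- A reader might infer that restarts go unrecorded. Drop criteria 2 and 3 imply that the team will learn of them. What is missing is any statement that date and reason are recorded, or that a count will be reported.
- A reader might infer that the comparison with 68% is shown to be biased in favour of EnBrace. The downward direction holds only against the same cohort without restarts. How the historical study handled restarts is not given, so the net effect on the comparison is unknown.
- A reader might infer that one such woman could turn a negative result positive. Under an assumed one-sided exact test against 68%, 3 of 10 gives p = 0.0155 and 4 of 10 gives p = 0.0637. The plan names no test, and against 43% the same 3 of 10 gives p = 0.31.

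**Conclusion.** The point holds as a gap in what the Group 1 rate can be attributed to. Applied literally, the stated rules credit EnBrace with a non-relapse reached on a resumed antidepressant, and Section V does not set that woman apart. If the benchmark is the cohort risk without restarts and antidepressants do not raise risk, the effect on the MINI-only rate is downward or nil. In the worked example it is between 0 and 12.8 points for two women.

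The size rests on assumed values for the number of restarters and their risk with and without the drug, on which of the two quoted benchmarks applies, and on carrying that benchmark over to 12 weeks. It is small next to the sampling error of ten women. The stakes are minor, but the remedy is cheap and the restart information is easier to collect during the study than to reconstruct afterwards.

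Section V is also silent on how women removed under the drop criteria are counted. This point does not rely on that.

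**What to change.** At each visit, record whether an antidepressant has been restarted, with the date and the reason (depressive symptoms, or while well). After a symptomatic restart, continue the MINI to week 12.

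In Section V:

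- Keep MINI-only relapse as the main Group 1 rate.
- Report the number of symptomatic restarts beside it.
- Add one sensitivity rate that counts the first of a MINI episode or a restart for depressive symptoms.
- State how the historical study handled restarts, if this can be established.

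Drop criterion 2 need not change. The cost is one question per visit, a few sentences in Section V, and a second rate that will count some restarts after which no episode would have followed (2 points too high in the worked example, 70% against 68%).
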